2.3 Patient disposition, demographics and other baseline characteristics

Demographic and other baseline data including disease characteristics will be listed and summarized descriptively by cohort and treatment group for the FAS.

Categorical data will be presented as frequencies and percentages. For continuous data, mean, standard deviation, median, minimum, and maximum will be presented. For selected parameters, the 25th and 75th percentiles will also be presented.

Medical history/current medical conditions and adverse events will be coded using the Medical Dictionary for Regulatory Activities (MedDRA) terminology. Relevant medical histories and current medical conditions at baseline will be summarized for FAS by cohort, treatment group system organ class and preferred term.

In addition, all medications and significant non-drug therapies administered to a mother (or the person) providing breastmilk to a patient before the patient enters the study and starts treatment with study drug will be summarized under Concomitant medications/Significant non-drug therapies prior to start of study drug.

2.3.1 Patient disposition

The number and percentage of patients screened will be presented.

The number and percentage of patients who completed and who discontinued prematurely will be presented for each epoch (treatment and follow-up) by cohort for each treatment group.

For each protocol deviation, the number and percentage of patients for whom the deviation applies will be tabulated.

Data will be presented using FAS.

2.4 Treatments (study treatment, rescue medication, concomitant therapies, compliance)

2.4.1 Study treatment / compliance

Number and percentage of tablets taken will be presented by cohort and treatment group. The percentage will be calculated based on the planned number of tablets per treatment group. Both number and percentage mean, standard deviation, median, 25th and 75th percentiles, minimum, and maximum will be presented.

Planned number of tablets in a treatment group = planned number of days of dosing x number of tablets to be administered per day in that treatment group.

For example, planned number of tablets for starting dose level 2 is 3 (planned number of days of dosing) x 2 (number of tablets) x 2 (twice a day) = 12 tablets.

Percentage of tablets taken will be calculated as Number of tablets consumed/Number of tablets planned x 100.

Compliance will be categorized by < 80 % and >=80 % of tablets taken and summarized by cohort and treatment group.

Number and percentage of patients with study drug vomiting and dose replacement will be presented by cohort and treatment group.

Safety set will be used.

2.4.2 Prior, concomitant and post therapies

Concomitant medications and significant non-drug therapies prior to and after the start of the study treatment will be listed and summarized according to the latest version of WHO Drug Reference List dictionary which employs the Anatomical Therapeutic Chemical (ATC) classification system. The summaries will be presented by cohort, treatment group, ATC class and preferred term (PT). Data will be summarized as frequencies and percentages. Safety set will be used.

2.5 Analysis of the primary objective

A pharmacokinetic parameter for artemether after the first dose, artemether C_{max} (ART C_{max}) will be assessed as the primary endpoint.

2.5.1 Primary endpoint

ART C_{max} (artemether C_{max}) will be calculated using the peak plasma concentration of artemether following the first dose. For artemether, ART C_{max} is determined by collecting samples at 1h and 2h after first dose and ART C_{max} represents the higher concentration between the concentrations at 1 hour and 2 hours post first dose.

The PK analysis set will be used.

2.5.2 Statistical hypothesis, model, and method of analysis

Ninety percent (90%) 2-sided confidence intervals for ART C_{max} for the geometric mean will be presented by cohort and treatment group. Calculation will be based on the log normal distribution. The study objective will be considered to be met if 90% CIs for ART C_{max} contain the desired values based on historical data especially those from children $\geq 5-15$ kg BW in Study B2303. The desired values are displayed in the Appendix in Table 5-7.

2.5.3 Handling of missing values/censoring/discontinuations

Patients without sufficient PK concentrations for the derivation of ART C_{max} will not be included in the analysis.

2.5.4 Supportive analyses

Sensitivity analyses

Ninety percent (90%) 2-sided confidence intervals for the geometric mean of ART C_{max} will be calculated based on the log normal distribution by cohort and treatment group using the PPS. Patients with missing ART C_{max} will be excluded from the analysis.

Supportive analyses

If there are treatment groups that are used for multiple cohorts, ninety percent (90%) two -sided confidence intervals for the geometric mean of ART C_{max} will be calculated for these treatment groups based on the log normal distribution using the PK set by pooling data from all cohorts.

2.6 Analysis of the key secondary objective

2.6.1 Key secondary endpoint

The Day 8 (168 h) lumefantrine concentration (LUM C_{168h}) is a key secondary endpoint.

2.6.2 Statistical hypothesis, model, and method of analysis

Ninety percent (90%) 2-sided confidence intervals for the geometric mean will be calculated for Day 8 (168 h) lumefantrine concentration based on the log normal distribution by cohort and treatment group using the PK analysis set.

LUM C_{168h} is considered to be comparable with historical data if the upper limit of 90% confidence interval is not less than the Historical values. The desired historical values are displayed in the Appendix in [Table 5-7](#).

2.6.3 Handling of missing values/censoring/discontinuations

Patients without evaluable Day 8 lumefantrine concentrations will be excluded from the analysis.

2.7 Analysis of secondary efficacy objective(s)

2.7.1 Secondary endpoints

Secondary Efficacy endpoints are:

- PCR-corrected ACPR at Day 15, Day 29 and Day 43.
- Uncorrected ACPR at Day 8, Day 15, Day 29, and Day 43.
- Incidence rate of recrudescence and new infections at Days 15, 29 and 43
- Parasite and Fever clearance Times (PCT and FCT)

2.7.2 Statistical hypothesis, model, and method of analysis

There are no pre-specified hypotheses for secondary endpoints. Model and method of analysis are presented in the following sub-sections by topic.

If there are treatment groups that are used for multiple cohorts, descriptive statistics will be calculated for these treatment groups by pooling data from all cohorts.

2.7.2.1 PCR-corrected ACPR and uncorrected ACPR

At each visit, the ACPR rate with 95% 2-sided confidence intervals will be provided using the Clopper-Pearson method for each treatment group by cohort using PPS for PCR-corrected ACPR and FAS for uncorrected ACPR.

Data will be handled as follows:

- Treatment failures after 7 days (i.e., Study Day 8) due to new infections based on PCR genotyping are not considered as failure for PCR-corrected analyses.

- For uncorrected ACPR, patients will be treated as failure on and after the visit when a reinfection with *P. falciparum* or other species is detected (which might be either recrudescence or a new infection).
- Patients who received rescue medication for the treatment of *P. falciparum* malaria (except for the treatment of a new infection) will be considered treatment failures. Patients who received other concomitant medication having an effect on malaria for reasons other than rescue therapy e.g., for the treatment of *P. vivax* (e.g., primaquine, certain antibiotics (sulfonamides, tetracycline, etc.) will be considered in the analysis as if they had not taken the drug.
- Patients will be counted as failure at a visit (e.g. Study Day 15, etc.) if (a) they did not have a parasite count, i.e., missing parasite count at that visit unless these patients could be classified as cured based on absence of parasitaemia (parasite count = 0) at a later time (e.g., Study Day 29), or (b) they did not have valid PCR evaluations at baseline and the visit if parasitaemia was present at that time (e.g., Study Day 15).
- For intermediate missing data, (a) once a patient experienced a treatment failure at a timepoint (eg. Day 15), the patient is considered as treatment failure at all later timepoints (eg. Day 29), (b) if a patient is considered as cured at a timepoint (eg. Day 29), the patient is considered as cured at earlier timepoints (eg. Day 15).

2.7.2.1.1 Analysis of PCR-corrected ACPR using Kaplan-Meier method

In addition, PCR-corrected ACPR rate will be calculated and plotted using the Kaplan-Meier method ([Stepniewska and White 2006](#); [WHO 2015](#)) for each treatment group by cohort in the FAS for Study Day 29 and 43. The PCR-corrected ACPR rate at Study Day 29 (43) is estimated by the survival function at Study Day 29 (43).

Event is defined as treatment failure. The censoring rules are as follows:

- For patients who do not experience treatment failure and do not have Study Day 43 data, time to treatment failure is considered as censored at the time of last parasitaemia assessment.
- Patients who had a new infection with *P. falciparum* or other species without *P. falciparum* recrudescence on or after Study Day 8 will be censored at the time of the first PCR that indicate the infection.
- Patients who took antimalarial medications for reinfection or reasons other than rescue medication given for *P. falciparum* related treatment failure will be censored at the first time of such antimalarial medications.
- Time to treatment failure (event or censored) will be truncated at Day 43 to avoid sudden drop in number of patients at risk after Day 43.

2.7.2.1.2 Sensitivity Analysis

For the CSR, not for IA01, there will be a sensitivity analysis of ACPR wherein patients are excluded from the PPS if they have a new infection prior to Day 29.

2.7.2.2 Recrudescence and new infection

New infection is defined as appearance of asexual parasites after clearance of initial infection with a genotype different from those parasites present at baseline. New infection must be confirmed by PCR analysis.

Recrudescence is defined as appearance of asexual parasites after clearance of initial infection with a genotype identical to that of parasites present at baseline. Recrudescence must be confirmed by PCR analysis.

Incidence rates of recrudescence and new infection at Days 15, 29 and 43 will be estimated by Kaplan-Meier method based on the subset of FAS patients who have clearance of initial infection by Day 7. Time to event (recrudescence or new infection) will be calculated from the time of first study medication to the date of first event if a patient experiences the event and be censored at the time of last parasite assessment if a patient does not experience the event.

Patients with new infection will be censored at the time of first new infection when analyzing time to recrudescence. Patients with recrudescence will be censored at the time of first recrudescence when analyzing time to new infection. Undetermined treatment failures due to missing PCR data will be considered as censored at the time of treatment failure.

Time (event or censored) will be truncated at Day 43 to avoid sudden drop in number of patients at risk after Day 43.

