6.2.3 Rescue medication

The following circumstances warrant discontinuation of study treatment (during the treatment period) and the implementation of rescue medication by the investigator (Commencement of rescue medication may occur after the start of study drug and up to Day 43):

Early Treatment Failure (ETF)

- Development of danger signs or severe malaria on Day 2, Day 3, Day 4 in the presence of parasitemia.
- Parasitemia on Day 3 higher than Day 1 count irrespective of axillary temperature.
- Parasitemia on Day 4 with axillary temperature $\geq 37.5^\circ$.
- Parasitemia on Day 4 equals to or more than 25% of count on Day 1.

Late Clinical Failure (LCF)

- Development of danger signs or severe malaria on any day from Day 5 to Day 43 in the presence of parasitemia without previously meeting any of the criteria of Early Treatment Failure.
- Presence of parasitemia and axillary temperature $\geq 37.5^\circ$ on any day from Day 5 to Day 43 without previously meeting any of the criteria of Early Treatment Failure.

Late Parasitological Failure (LPF)

- Presence of parasitemia on any day from Day 8 to Day 43 and axillary temperature $< 37.5^\circ$ without previously meeting any of the criteria of Early Treatment Failure or Late Clinical Failure.

Rescue treatment involves therapy with an effective antimalarial available locally as per local medical practice or National Treatment Guidelines. Administration may be oral or parenteral depending on the subject's clinical condition. Rescue treatment will not be considered study medication. The exact rescue regimen and route of administration must be recorded on the appropriate CRF.

Patients will be monitored, either in clinic, or via home visits for the duration of treatment to ensure adherence to the rescue medication therapy. These patients will not discontinue the study (i.e., all the examinations as per the assessment schedule and all CRF for this patient will need to be completed), and they will not be replaced (unless the PK data cannot be properly analyzed due to treatment schedule discontinuation).

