2.7.2.3 Parasite clearance time (PCT) and fever clearance time (FCT)

Descriptive statistics (mean, standard error, median, quartiles) will be presented for each treatment by cohort using the Kaplan-Meier method based on the FAS. Kaplan-Meier curves will be provided.

Parasite clearance time

PCT will be calculated based on uncorrected parasite counts. Patients without parasite clearance for whatever reason will be censored at the time of last parasite assessment.

Fever clearance time

Patients who had no fever at pre-dose will not be included in the analysis of FCT. Patients without fever clearance for whatever reason will be censored at the time of last temperature assessment.

Handling of missing values/censoring/discontinuations

In case that a patient receives rescue medication before (parasite or fever) clearance, the time to event will be censored at the first use of rescue medication.

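### Recrudescence and new-infection incidence is not censored at non-study antimalarials, and Day 7 clearance is not required to precede rescue, unlike the neighbouring time-to-event analyses

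*SAP*

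**What the plan says.** **The endpoint.** SAP 2.7.2.2 estimates incidence at Days 15, 29 and 43 by Kaplan-Meier, "based on the subset of FAS patients who have clearance of initial infection by Day 7". Time runs from the first dose and will "be censored at the time of last parasite assessment if a patient does not experience the event". The SAP then adds three rules that protocol 12.5.1 does not have:
- cross-censoring between the two types of recurrence ("Patients with new infection will be censored at the time of first new infection when analyzing time to recrudescence", and the reverse);
- "Undetermined treatment failures due to missing PCR data will be considered as censored at the time of treatment failure";
- truncation at Day 43.

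No rule in either section mentions rescue medication or any other antimalarial.

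**Who stays in follow-up.** Protocol 6.2.3 states that "Commencement of rescue medication may occur after the start of study drug and up to Day 43". Its grounds include early treatment failure on Days 2 to 4. Protocol 6.7.2 adds rescue when a repeat dose is vomited, which needs no parasitological failure. Rescued infants keep the full assessment schedule (protocol 6.2.3). So do infants given other antimalarials, or antimicrobials with antimalarial activity (protocol Table 6-2). The FAS (SAP 2.2) asks only for some study drug and *P. falciparum* at screening, so none of these infants is removed.

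**The neighbouring analyses.**
- Kaplan-Meier PCR-corrected ACPR (SAP 2.7.2.1.1): treatment failure is the event. Patients taking antimalarials for reinfection, or for reasons other than rescue of a *P. falciparum* failure, "will be censored at the first time of such antimalarial medications".
- Parasite and fever clearance times (SAP 2.7.2.3): where rescue comes before clearance, "the time to event will be censored at the first use of rescue medication".
- ACPR proportions (SAP 2.7.2.1): patients who take drugs with an antimalarial effect for non-rescue reasons "will be considered in the analysis as if they had not taken the drug".

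**The concern.** A recurrence rate is meant to describe what happens after the study regimen clears the infection. An infant who has moved to another antimalarial is under that drug's protection, and a recurrence-free Day 43 then says little about artemether-lumefantrine. With the last assessment as the default censoring time and follow-up continuing to Day 43, the rule credits that period to the study regimen.

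Three groups are exposed:
1. infants rescued after vomiting a repeat dose;
2. early failures who are rescued and then clear by Day 7, unless the PCT rescue rule is read across;
3. infants given another antimalarial, or an antimicrobial with antimalarial activity, for some other reason.

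At stake are named secondary efficacy endpoints in cohorts of about 22, where two or three infants move a percentage visibly. The text also leaves the risk set open, so two programmers could build different ones.

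**Working it through.** **Step 1: compare the rules.** The plan states no rate, sample size or power for this endpoint, so there is no figure to reproduce. The check is mainly of the text.

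| Situation | Incidence (2.7.2.2) | Kaplan-Meier ACPR (2.7.2.1.1) | PCT (2.7.2.3) |
|---|---|---|---|
| Rescue before clearance, then clear by Day 7 | Not stated; if admitted, followed to last assessment | Event if classed as treatment failure | Censored at rescue |
| Rescue after clearance for a vomited repeat dose | Followed to last assessment | Not named separately | Clearance already counted |
| Other antimalarial for another reason | Followed to last assessment | Censored at that drug | Not addressed |
| Rescue for a recurrence after clearance | Event, cross-censored, or censored as undetermined | Event, or censored if new infection | Clearance already counted |

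The last row is not a gap. The first three rows are where follow-up under another drug can enter.

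**Step 2: size, on assumed counts.** Inputs:
- *n*, infants at risk: 22, the planned cohort size in SAP 3.1.2 (16/(1 − 0.25) = 21.3, rounded up). That all 22 enter the risk set is an assumption. 16 is used as a second case.
- *d*, recrudescences among infants who did not switch: assumed 2 or 3, all at Day 29.
- *k*, infants who switched before Day 29: assumed 1 to 4.
- *r*, recurrences among those *k*: assumed 0 at first.

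With otherwise complete follow-up, Kaplan-Meier reduces to a proportion:
- under the present rule: (d + r)/n;
- after censoring or excluding switched infants: d/(n − k).

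| n | d | Present rule | k = 1 | k = 2 | k = 3 | k = 4 |
|---|---|---|---|---|---|---|
| 22 | 2 | 9.1% | 9.5% | 10.0% | 10.5% | 11.1% |
| 22 | 3 | 13.6% | 14.3% | 15.0% | 15.8% | 16.7% |
| 16 | 2 | 12.5% | 13.3% | 14.3% | 15.4% | 16.7% |
| 16 | 3 | 18.8% | 20.0% | 21.4% | 23.1% | 25.0% |

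Censoring at Day 3, exclusion at entry and censoring at Day 15 all give the same values, because every assumed event falls at Day 29. With k = 0 nothing changes. With r = 0 the relative understatement is k/n: 1/22 = 4.5% to 3/22 = 13.6% for one to three infants.

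**Step 3: direction.** The present estimate is a weighted mix:

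(d + r)/n = [(n − k)/n] × [d/(n − k)] + (k/n) × (r/k)

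It is too low only if r/k is below d/(n − k). For n = 22, d = 2, k = 3, the threshold is 2/19 = 10.5%. One recurrence among the three gives r/k = 33%, and the present rule then gives 3/22 = 13.6% against 10.5%. The sign reverses.

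**The case against.** **Entry of infants cleared by rescue rests on silence.** A reader might infer that the plan admits infants cleared by the rescue drug. It does not say so. SAP 2.1.1.1 defines parasite clearance through PCT, and 2.7.2.3 censors PCT at rescue given before clearance. If clearance by Day 7 means a PCT event by Day 7, infants rescued before clearance never enter, and figures resting on them fall away. This stands as a reasonable reading, but 2.7.2.2 does not refer to the PCT rule.

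**Most rescue is already handled.** A reader might conclude that rescue is ignored altogether. The early, late clinical and late parasitological failure criteria all require parasitaemia, so rescue for a recurrence after clearance coincides with an event or an existing censoring point. This stands.

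**There is a precedent for ignoring other drugs.** The ACPR proportions do so explicitly for non-rescue drugs. For that group, censoring is a choice of estimand rather than the repair of an outright error. This also stands, but 2.7.2.2 declares no such choice, and the closest time-to-event analysis censors.

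**A firm downward bias of 5% to 14% is not supported.** That range needs assumed counts and no recurrence after rescue. Rescued infants remain under assessment, so a recurrence in them would count as an event. Even on those assumptions, 9.1% against 10.5% is 1.4 points, while the exact 95% interval for 2/22 is 1.1% to 29.2%.

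**Failures are not hidden.** Patients rescued for *P. falciparum* malaria, except for a new infection, count as failures in the ACPR proportions, and treatment failure is the event in Kaplan-Meier ACPR on the FAS. Poor performance would show there.

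**Conclusion.** The point holds as a gap in the stated censoring and entry rules. SAP 2.7.2.2 and protocol 12.5.1 allow follow-up under a non-study antimalarial to count as time on the study regimen. That is inconsistent with 2.7.2.1.1 and 2.7.2.3. For infants rescued before clearance, it depends on the PCT rescue rule not being read across. For infants rescued for vomiting after clearance, and for those given other antimalarials for other reasons, it follows from the text directly.

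If the other drug suppresses recurrence, incidence is understated. On the assumed case of 22 at risk, 2 recrudescences and 1 to 3 switched infants without recurrence, 9.1% becomes 9.5% to 10.5%. The documents supply none of these event or switch counts, and recurrence among rescued infants could reverse the direction. The same reasoning applies to new infections. The endpoint is secondary, descriptive and without a pre-specified hypothesis (SAP 2.7.2), and the primary artemether Cmax analysis is unaffected. This is an inexpensive correction, not a threat to the trial's main conclusion.

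**What to change.** In SAP 2.7.2.2 and protocol 12.5.1:
1. Define clearance by Day 7 as a PCT event under SAP 2.1.1.1 and 2.7.2.3, so that an infant rescued before clearance does not enter the risk set.
2. Censor at first use of any non-study antimalarial that is not given for the event itself, in line with 2.7.2.1.1.
3. Report how many infants are excluded or censored for these reasons, and give the present uncensored version as a sensitivity analysis.

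The cost is a few sentences. Rescue and concomitant medication are already recorded (protocol 6.2.1 and 6.2.3), and the neighbouring analyses already need the dates. No clinical procedure changes. The downsides are a slightly smaller risk set and the possibility that censoring at rescue is itself informative, since early failures may differ in their risk of recrudescence. That is why the uncensored version should be kept alongside.

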In addition, PCR-corrected ACPR rate will be calculated and plotted using the Kaplan-Meier method ([Stepniewska and White 2006](#); [WHO 2015](#)) for each treatment group by cohort in the FAS. Treatment failure is the event for analysis. For patients who do not experience treatment failure and do not have Study Day 43 data, treatment failure is considered as censored. The PCR-corrected ACPR rate at Study Day 29 is estimated by the survival function at Study Day 29. Patients who had a new infection with *P. falciparum* or other species without *P. falciparum* recrudescence on or after Study Day 8 will be censored at the time of the first PCR that indicate the infection; patients who took antimalarial medications for reinfection or reasons other than rescue medication given for *P. falciparum* related treatment failure will be censored at the first time of such antimalarial medications; other patients without treatment failure will be censored at the time of last parasitemia assessment.

Recrudescence and new infection

New infection is defined as appearance of asexual parasites after clearance of initial infection with a genotype different from those parasites present at baseline. New infection must be confirmed by PCR analysis.

Recrudescence is defined as appearance of asexual parasites after clearance of initial infection with a genotype identical to that of parasites present at baseline. Recrudescence must be confirmed by PCR analysis.

Incidence rates of recrudescence and new infection at Days 15, 29 and 43 will be estimated by Kaplan-Meier method based on the subset of FAS patients who have clearance of initial infection by Day 7. Time to event (recrudescence or new infection) will be calculated from the time of first study medication to the date of first event if a patient experience the event and be censored at the time of last parasite assessment if a patient does not experience the event.

Parasite clearance time (PCT) and fever clearance time (FCT)

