5.8 Rule of exclusion criteria of analysis sets

Table 5-7 Protocol deviations and non-PD criteria leading to exclusion from analysis sets ce values for PK analyses

Analysis Set	PD (description and ID) that causes subjects to be excluded	Non-PD criteria that cause subjects to be excluded
FAS	Informed Consent for study participation not obtained (INCL05) Plasmodium falciparum not present as parasite species at Screening visit (INCL04)	No study drug taken
SAF	Informed Consent for study participation not obtained (INCL05)	No study drug taken
PPS	Baseline Plasmodium falciparum parasite count is not ≥ 500 and $< 100,000/\mu\text{L}$ at screening visit for patients in Cohort 1 (INCL04A) Baseline Plasmodium falciparum parasite count is not ≥ 100 and $< 100,000/\mu\text{L}$ at	Not in FAS Did take less than 80% of planned study medication (see Section 2.4.1) PCR corrected cure status at Day 29 can not be defined Not classified as non-responder before Day 8, no positive blood smear parasite on Day 8

Analysis Set	PD (description and ID) that causes subjects to be excluded	Non-PD criteria that cause subjects to be excluded
	screening visit for patients in Cohort 2 (INCL04B)	onwards, and blood smear parasite result is missing at Day 29.
	Prohibited concomitant anti-malarial medication administered without experiencing ETF, LCF, LPF (PROH02)	Not classified as non-responder before Day 8, have at least one positive blood smear parasite result between Day 8 and Day 29 which cannot be determined as recrudescent or new infection based on PCR genotyping.
	Prohibited concomitant non-malaria medications with potential impact on efficacy/antimalarial activity (PROH01A)	
	Presence of another critical condition (EXCL06)	
PK		Not in FAS
		No evaluable PK parameter data available

6 References

Stepniewska K, White NJ (2006) Some considerations in the design and interpretation of antimalarial drug trials in uncomplicated falciparum malaria. *Malar J*; 5: 127.

World Health Organization (2015) Guidelines for the treatment of malaria. Third Edition.

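### Recurrences without PCR data are events in neither the recrudescence nor the new-infection curve, so both incidences are low in expectation even if PCR is missing at random

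*SAP*

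**What the plan says.** SAP 2.7.2.2 defines two events among full-analysis-set infants who cleared the initial infection by Day 7. Both definitions depend on genotyping: "Recrudescence must be confirmed by PCR analysis" and "New infection must be confirmed by PCR analysis". Each incidence is estimated by Kaplan-Meier at Days 15, 29 and 43, with the other type censored: "Patients with new infection will be censored at the time of first new infection when analyzing time to recrudescence", and "Patients with recrudescence will be censored at the time of first recrudescence when analyzing time to new infection". For a recurrence that has no type, the rule is "Undetermined treatment failures due to missing PCR data will be considered as censored at the time of treatment failure".

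Protocol 12.5.1 contains the same PCR-confirmation requirement for both events but no separate rule for untyped recurrences. It says only that a patient will "be censored at the time of last parasite assessment if a patient does not experience the event".

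Other parts of the SAP handle the same infant differently:

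- **SAP 2.7.2.1 (ACPR):** an infant counts as a failure at a visit if "they did not have valid PCR evaluations at baseline and the visit if parasitaemia was present at that time".
- **SAP 5.8 (per-protocol set):** an infant not already a non-responder before Day 8 is excluded if there is a positive smear between Day 8 and Day 29 "which cannot be determined as recrudescent or new infection based on PCR genotyping".

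The only sensitivity analysis in this part of the SAP (2.7.2.1.2) concerns ACPR and new infections before Day 29. No bounds and no any-recurrence curve are planned for the two incidences.

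**The concern.** Ordinary censoring says that follow-up stopped before the event and that the event might have come later. Here follow-up stops because the event happened. Parasites were seen again after clearance, and only the label is missing. The infant counts in the risk set up to that time, but the event never reaches the numerator of either curve.

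At stake is how two secondary efficacy results read. Protocol 1.1 describes lumefantrine as the component that prevents recrudescence, and the 1:12 ratio is new. With about 22 infants per cohort, one event at full risk is 1/22, or 4.5 percentage points. One or two untyped recurrences would visibly change the reported incidence, and as planned they change it only downwards.

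**Working it through.** The plan states no recurrence incidence and no PCR-failure rate, so there is no figure of its own to reproduce. The rules come from SAP 2.7.2.2 and the cohort size of about 22 from SAP 1.1. All event rates and untyped fractions below are assumptions.

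**Step 1: direction.** A typed recurrence is an event in one curve and is censored at the same time in the other. An untyped one is censored at that time in both. The risk sets are the same either way, so losing the label can only remove an event. Each untyped infant lowers the curve of its true type and leaves the other unchanged. If PCR failure is unrelated to type, untyped infants include both types and both curves are low in expectation.

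**Step 2: size in closed form.** Let H be the cumulative cause-specific hazard to Day 43 and m the fraction of recurrences untyped at random. The complete-PCR target is 1 − exp(−H). The SAP rule estimates 1 − exp(−(1 − m)H). Assume crude Day-43 risks of 10% (recrudescence) and 20% (new infection):

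- Total hazard = −ln(0.70) = 0.3567, split 1:2 into 0.1189 and 0.2378.
- Complete PCR: 1 − exp(−0.1189) = 11.2% and 1 − exp(−0.2378) = 21.2%.
- m = 20%: 1 − exp(−0.0951) = 9.1% and 1 − exp(−0.1902) = 17.3%.

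The relative losses are 19% and 18%, close to m.

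**Step 3: size against sampling error.** Simulated trials of 22 infants had films at Days 15, 29 and 43 and PCR missing at random. Crude recrudescence/new-infection risks were 5%/25%, 10%/20%, 10%/30% and 5%/40%. The shift is divided by the standard deviation of the complete-PCR estimate across trials.

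| Untyped | Recrudescence shift (SE) | New-infection shift (SE) |
|---|---|---|
| 10% | 0.10 to 0.15 | 0.2 to 0.3 |
| 20% | 0.21 to 0.30 | 0.4 to 0.7 |
| 30% | 0.31 to 0.46 | 0.7 to 1.0 |

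**Step 4: worked case (assumed counts).** Take 22 infants, all followed to Day 43: one recrudescence at Day 29, new infections at Days 29, 29, 43 and 43, and untyped recurrences at Days 29 and 43. At risk: 22 at Day 29 and 22 − 4 = 18 at Day 43.

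- SAP rule, recrudescence: 1/22 = 4.5%.
- SAP rule, new infection: 1 − (20/22)(16/18) = 19.2%.
- Both untyped counted as recrudescence: 1 − (20/22)(17/18) = 14.1%.
- Both untyped counted as new infection: 1 − (19/22)(15/18) = 28.0%.
- Any recurrence, which needs no typing: 7/22 = 31.8%.

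Here 2 of 7 recurrences (29%) are untyped, near the top of the assumed range. The planned figures, 4.5% and 19.2%, are the lower ends of 4.5% to 14.1% and 19.2% to 28.0%.

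**Step 5: literal protocol reading.** If the infant untyped at Day 29 stays at risk to Day 43 as a non-event, new infection is 1 − (20/22)(17/19) = 18.7%, slightly below the SAP's 19.2%.

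**The case against.** Much of the case for leaving the rule alone is sound.

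- **The SAP did not introduce the bias.** A reader might infer an undeclared departure from the protocol, because SAP 4 reports no change. The documents do not support that. Protocol 12.5.1 requires PCR confirmation for both events, so an untyped recurrence is already a non-event there. The SAP sets an earlier censoring time, which in the worked case gives a slightly higher estimate.
- **The ACPR rule is not contradicted.** A reader might set SAP 2.7.2.1 against 2.7.2.2. They define different endpoints, and PCR-corrected ACPR uses the per-protocol set, from which SAP 5.8 generally removes infants with an untyped positive smear by Day 29. The handling is inconsistent across analyses, but no rule is broken.
- **The two incidences need not sum to less than the recurrence proportion.** Each curve censors the other type, so each complete-PCR value exceeds the crude risk (11.2% against 10% in Step 2), and the two do not add. In that example the reported figure falls below crude risk only above about 11% untyped for recrudescence and 6% for new infection. This is a separate, opposing effect and does not justify the rule.
- **Untyped cases may be few.** Protocol 8.3 plans a baseline sample for every eligible infant and reference-laboratory genotyping at failure.
- **Uncorrected ACPR keeps these infants as failures.** This is true, but it also counts missing films as failures and is not restricted to infants who cleared by Day 7. It is not a recurrence incidence.

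What remains is the effect on the two incidences themselves, which no other planned analysis corrects.

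**Conclusion.** The point holds, at minor to moderate weight. As written, a recurrence with missing PCR data is an event in neither curve. Both incidences are therefore low in expectation against the plan's own Kaplan-Meier quantity with complete PCR, and random missingness does not remove this. The direction is certain. The size rests on assumed rates: a relative loss near the untyped fraction, or about 0.1 to 0.5 standard errors for recrudescence and 0.2 to 1.0 for new infection at 10% to 30% untyped with 22 infants.

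Two limits apply. A single untyped infant lowers only one curve, so in a given trial one of the two may be unaffected. The SAP sentence also names missing PCR data only; a PCR that was run but gave no answer would become a non-event through the general censoring rule. These are descriptive secondary endpoints without pre-specified hypotheses, and the primary endpoint, artemether Cmax, is untouched.

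**What to change.** In SAP 2.7.2.2, keep the typed-only estimates and add:

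1. A Kaplan-Meier incidence of any recurrence at Days 15, 29 and 43, in the same infants who cleared by Day 7, with typed and untyped recurrences all counted as events.
2. The number of untyped recurrences by cohort and treatment group, covering PCR that is missing and PCR that is indeterminate.
3. Both bounds for each type-specific incidence: all untyped recurrences counted as recrudescence, then all counted as new infection.

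In the worked case the report would read: recrudescence 4.5% to 14.1%, new infection 19.2% to 28.0%, any recurrence 31.8%, two untyped.

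The cost is SAP wording and a few table rows, with no new data collection. The downside is a wider and less favourable range for recrudescence. If every recurrence is typed, the bounds collapse to the planned estimates.
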